Sample size. A meta-analysis of 58 studies indicates that the overall prevalence of postpartum depression is 17% (95% CI: 0.15–0.20) (53). This estimate falls within previously published estimates of 13%–19.2% (54, 55) and is similar to Hahn-Holbrook's 2018 finding of 17.7%. In-person interventions using the *Mother & Babies* course reported moderate effect sizes (OR = 0.28 (0.08-0.94) (22) and OR = 0.45 (0.19-1.10) (24)). Fully web-based without nurse-based telephone support reported small to moderate effect sizes (40). Given that the proposed intervention is offered virtually with nurse-based telephone support, we calculated a sample size that allows us to detect a moderate decrease in rates of clinical depression. We anticipate that 20% of pregnant women in the control group will have an EPDS score ≥ 13 at postpartum. A total of 500 pregnant women (250 per arm) is needed to detect an absolute reduction of 10% (i.e., 20% of women with EPDS ≥ 13 in the control arm versus 10% in the intervention arm) with 80% of power and a 2-tailed alpha of 5%. The sample size includes an attrition rate of 10% for 3 months' postpartum and another 10% between 3 and 6 months' postpartum. Based on our experience with pregnant women and the intervention (see Section about Pilot Study), the 10% attrition estimate is conservative. As most of the secondary

outcomes are continuous, the sample size provides enough power to detect small to moderate effect sizes using a 2-tailed alpha of 1% to account for multiple tests.

Compliance. We conducted a feasibility pilot study including 17 pregnant women. All began to read the online material and 2 refused further participation after 2 telephone calls, a dropout rate of 11.7%. We therefore expect that 80-90% of the intervention group will read at least some of the intervention material. Intervention compliance will be defined as completion of a minimum of 6/8 online modules and 6/10 telephone follow-ups. Compliance will be monitored automatically online and by nurses during telephone calls. Weekly text reminders will be sent out to maximize compliance (see details in Appendix H).

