Primary outcome. Maternal depression at 3 months' postpartum was chosen as the primary outcome to: 1) ensure comparability to other perinatal trials (60-67) and 2) to reduce potential biases induced by attrition. The primary outcome will be the proportion of women with EPDS scores above the clinical cut-off for depression (EPDS \geq 13)). Differences between experimental and control groups will be analyzed at T₁ (3 months' postpartum) and again at T₂ (6 months' postpartum, secondary outcomes). The EPDS is an internationally recommended 10-item self-report scale that assesses depressive symptoms on a 4-point scale; scores range from 0 to 30 with higher scores representing higher symptomatology. More than 80% of perinatal depression studies use self-report measures (73) and the majority use the EPDS. The EPDS was created to counter the limitations of other well-established depression scales when used during the perinatal period. It has been validated by standardized psychiatric interviews with large sample sizes and has well-documented reliability and validity of over 11 languages (50, 74). Participants will fill out the EPDS at 3 assessment times: baseline (T₀, as part of inclusion criterion), T₁, and T₂.

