Economic evaluation. Service utilization will be measured using a slightly modified version of the **Health Service Utilization and Cost of Care Questionnaire** (105) to assess childcare expenses and travel costs incurred by patients to obtain care. Costs of administering the intervention include a) recruiting and training of nurses, b) nurses' time to provide the intervention, and c) supervision of nurses.

Planned Analyses

Data will be analyzed using SAS software using an intent-to-treat approach. A two-sided significance level of 0.05 will be used for the primary outcome; a significance level of 0.01 (two-sided) will be used for secondary and other outcomes to account for multiple outcomes. Demographic and other baseline variables will be compared between study groups using descriptive statistics (mean, standard deviation, proportions).

For the primary outcome, a two-sample sided test of proportion (chi-square test) will be used to compare the difference in the proportion of women with EPDS in the clinical range (> 13) at 3 months' postpartum. The same approach will be used for the 6-month assessment (secondary outcome). These analyses will be supplemented by an analysis using EPDS scores, where the baseline EPDS score will be used as covariate in an ANCOVA model including the 3- and 6-month EPDS scores. With this model, we will obtain 95% confidence intervals of EPDS score differences between intervention arms at 3 and 6 months' postpartum. Sensitivity analyses will be performed to investigate the potential bias introduced

by attrition. A method based on inverse-probability-of-attrition weights (IPAWs) will be used (101, 102).

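### The primary chi-square could be pre-specified as adjusted for screening EPDS at no cost; the gain in power is under one point, and the plan is not in error without it

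*Combined protocol and SAP*

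**What the plan says.** All references are to the combined protocol and SAP.

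- **Planned Analyses, primary outcome:** "a two-sample sided test of proportion (chi-square test) will be used to compare the difference in the proportion of women with EPDS" above the cut-off at 3 months. No covariate is named. The test level is set by "A two-sided significance level of 0.05 will be used for the primary outcome".
- **Planned Analyses, supplementary analysis in the same paragraph:** "the baseline EPDS score will be used as covariate in an ANCOVA model" for the EPDS scores at 3 and 6 months, with 95% confidence intervals for the score differences.
- **Planned Analyses, secondary outcomes:** binary outcomes get a 95% CI for the difference in proportions. If the arms turn out unbalanced on baseline variables related to the primary and secondary outcomes, a logistic regression including those variables is used. Neither the variables nor a threshold for imbalance is listed.
- **Primary outcome:** "Participants will fill out the EPDS at 3 assessment times: baseline", 3 months and 6 months. The baseline value is the one used for eligibility.
- **Pregnant Women Recruitment:** the EPDS is taken by telephone as part of the eligibility check. Eligible women are then randomised and told their arm.
- **Partners Recruitment (closing paragraph):** recruited women are then sent the link to the baseline questionnaire. Website access opens once it is completed.
- **Sample:** only women scoring 9 to 12 enter.
- **Sample size:** the target is "20% of women with EPDS ≥ 13 in the control arm versus 10% in the intervention arm", and "The sample size includes an attrition rate of 10% for 3 months" plus a further 10% between 3 and 6 months.

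**The concern.** The test that decides the trial ignores a baseline score that is complete by design and fixed before allocation. The plan itself treats that score as worth adjusting for in the supporting model. A woman who enters at 12 starts nearer the cut-off of 13 than one who enters at 9, and an unadjusted comparison leaves that variation in the error.

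Two smaller matters follow:

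- The only route by which a covariate could reach the primary result is the imbalance rule. It leaves both the decision to adjust and the choice of variables until the data have been seen.
- The plan promises intervals for score differences and for binary secondary outcomes, but states none for the primary difference in proportions.

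At stake are a little precision, consistency between the primary and supporting analyses, and a primary effect estimate with an interval. The validity of the test is not at stake.

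**Working it through.** **1. Reproduce the plan's sample size.** Inputs from Sample size: 20% v 10%, two-sided 5%, 80% power. With pooled variance under the null and mean risk 0.15:

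n = [1.960·√(2·0.15·0.85) + 0.842·√(0.20·0.80 + 0.10·0.90)]² / 0.10² = (0.990 + 0.421)² / 0.01 = 199 per arm.

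Allowing 20% total loss: 199/0.80 = 249 per arm, 498 in all. The stated 500 is reproduced for an unadjusted test.

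**2. Power of the planned chi-square.** Power = Φ{[0.10·√n − 1.960·√0.255] / √0.25}.

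- 10% loss by 3 months, 250 × 0.9 = 225 per arm: (1.500 − 0.990)/0.5 = 1.02, so power is 84.6%.
- 20% loss, 200 per arm: (1.414 − 0.990)/0.5 = 0.85, so power is 80.2%.

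**3. How much screening EPDS can explain within 9-12.** The documents give no correlation between screening and 3-month EPDS. Assumptions: SD 5 and correlation r of 0.4 to 0.7 in unselected women, normal scores, and equal numbers entering at 9, 10, 11 and 12. Given entry score x, the 3-month score is normal with slope r in x and SD 5·√(1 − r²). The cut-point is set so that average risk matches the arm. R² on the binary outcome is the variance of the four risks divided by p(1 − p).

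| Arm risk | r | Risk at 9, 10, 11, 12 (%) | R² |
|---|---|---|---|
| 20% | 0.4 | 16.4, 18.7, 21.1, 23.7 | 0.5% |
| 20% | 0.7 | 12.4, 16.9, 22.2, 28.5 | 2.3% |
| 10% | 0.4 | 7.8, 9.2, 10.7, 12.4 | 0.3% |
| 10% | 0.7 | 5.4, 7.9, 11.2, 15.4 | 1.6% |

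For example, in the first row the mean squared deviation from 0.20 is 0.00074, and 0.00074/0.16 = 0.5%.

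**4. Power after adjustment.** Use effective n = 225/(1 − R²) in the formula of step 2.

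| R² | Effective n per arm | Power |
|---|---|---|
| 0 | 225 | 84.6% |
| 0.3% | 225.7 | 84.7% |
| 0.5% | 226.1 | 84.8% |
| 2.3% | 230.3 | 85.4% |

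The gain is 0.1 to 0.8 points.

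**5. Simulation check.** Logistic regression with standardisation to the risk difference, 3,000 runs per setting, entry scores uniform on 9-12. The ratio of adjusted to unadjusted standard error was 1.000, 0.998 and 0.989 for latent correlations within the band of 0.10, 0.15 and 0.25. Precision is not lost, and at most about 1% of the standard error is gained.

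**6. Which covariates are clean.** The telephone eligibility check covers EPDS, psychosis screening and substance use, and comes before randomisation. The GAD-7 and PRAQ-R2 are baseline measures that are not part of that check. As written, the baseline questionnaire is sent after the woman has been told her arm. Screening EPDS is therefore the only symptom score of the three that allocation cannot have influenced.

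**The case against.** The strongest reply is that nothing is broken. An unadjusted chi-square is valid in a 1:1 trial with no named stratification factor. It matches the basis of the sample size and needs only the 3-month EPDS. It has 84.6% power at the expected 3-month numbers. Screening EPDS takes four values, so adjusting for it changes almost nothing, and a missing confidence interval could be added in one sentence without any model. All of this stands. It sets the severity of the point, but does not remove the case for a change that costs nothing.

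Three stronger readings are tempting, and the documents do not support them.

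- **That several points of power are being lost.** A reader might add GAD-7 and PRAQ-R2 and suppose a joint R² of 5-10%. Power at 225 per arm would then be 86.4-88.2%, worth 12 to 25 extra women per arm (225/0.95 = 237; 225/0.90 = 250). That R² is not in the documents. It also depends on scales that, in the sequence described, are answered after the arm is known. Website access comes later, so the website cannot affect the answers, but knowledge of allocation could. Using them safely would mean changing the enrolment sequence, so that gain is not free.
- **That the ANCOVA shows the size of the gain.** The restriction to 9-12 and the dichotomised outcome both limit what baseline EPDS can add to the primary test.
- **That the plan is underpowered or wrong without adjustment.** Step 2 shows otherwise.

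It could also be said that the plan already has a logistic regression. That rule sits among the secondary outcomes, though its wording mentions the primary. It acts only on observed imbalance, so it is not pre-specified adjustment.

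**Conclusion.** The point holds as a minor improvement (could, not should). The primary test is unadjusted although a complete, pre-randomisation screening EPDS is available and is already used in the supporting model. The only other adjustment is left until imbalance is seen. Pre-specified adjustment would raise power at 225 per arm from 84.6% to about 84.7-85.4%. This rests on an assumed SD of 5 and a correlation of 0.4-0.7 in unselected women, neither of which the documents give. The stated 80% is met either way. The better reasons to make the change are that the model is fixed in advance, the primary and supporting analyses agree in their covariate, and the primary result gains an estimate with an interval.

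**What to change.** In Planned Analyses:

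- Make the primary analysis a logistic regression of EPDS ≥ 13 at 3 months on arm, with a linear term for the EPDS score recorded at the eligibility call.
- Report the standardised (marginal) risk difference with its 95% CI, so that the estimand remains the difference in proportions used for the sample size. Name the variance method.
- Keep the chi-square as a supporting analysis.
- State that the imbalance-triggered regression does not alter the primary analysis.
- Do not add GAD-7 or PRAQ-R2 under the current sequence of randomisation, disclosure and baseline questionnaire.

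The ≥ 13 above follows the Primary outcome and Sample size sections. The analysis sentence prints a strict inequality and should be brought into line at the same time.

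Cost: a few sentences of SAP text and a few lines of SAS. No new data, no extra women and no change to enrolment.

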During pregnancy and the postpartum period, women are at heightened risk of mental health problems, with 1/5 experiencing moderate to high levels of depressive symptoms (1, 2). Perinatal mental health problems often go unrecognized and undiagnosed (3), with fewer than 20% of symptomatic women receiving treatment (4). The cost of untreated maternal depression is estimated at over \$17,000 US per mother per year over the first five years of the child's life. In comparison, gestational diabetes costs up to \$3,300 per mother and occurs only during pregnancy (5). The consequences of untreated perinatal mood disorders include maternal psychological, social, occupational, and physical dysfunction (1, 2).

About 20-25% of pregnant women have subclinical levels of depression (Edinburgh Postnatal Depression Scale (EPDS) score 9-12) and 2/3 of these will go on to clinical postpartum depression (EPDS \geq 13) (6-8). Though ineligible for publicly funded clinical services, these women have poorer parenting/offspring outcomes (6). Fifteen meta-analyses (300+ studies) have documented associations between maternal depression and poor cognitive, behavioral, and emotional outcomes in the offspring, starting at birth and extending into adolescence (9-18). Preventive interventions and childhood assessments could inform the putatively causal role of maternal mental health on child development. In this study, we test an early pregnancy intervention and its impact on postpartum ages 3 and 6 months. The virtual or remote format of the intervention (online and telephone) is designed to overcome long-standing mental health management barriers.

Prevention of Postpartum Issues

There is growing evidence that the societal burden of perinatal mental health issues can be prevented. Most women with postpartum depression have symptoms during pregnancy (19, 20). High-risk women may be identified by simple screening (e.g., mobile phone) and EPDS (21), and prevention programs in person or in groups are effective (2). Recognizing potential for early prevention, the United States Preventive Services Task Force (2019) issued a level B recommendation “that clinicians provide or refer people who are at increased risk of perinatal depression to counseling interventions.” These include cognitive behavioral therapy (CBT) and interpersonal counseling, such as the existing, evidence-based *Mothers & Babies* program (22-25).

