We followed the USPSTF recommendation for the prevention of postpartum depression (2) by targeting pregnant women with moderate depressive symptoms, who could reasonably be considered as signaling distress or early signs of illness, are at high risk for postpartum depression, and are not eligible for specialized psychiatric care. Our program is a virtual and population-based preventive intervention, not a treatment for clinical depression, although it could reasonably be conceived as an adjuvant to psychiatric care.

Pregnant women inclusion criteria: Pregnant women (12-25 weeks' gestation), ages 14 years or older, with: 1) subclinical levels of depression (EPDS scores 9-12) and 2) ability to read and understand French.

Pregnant women exclusion criteria: 1) EPDS score in the clinical range (≥ 13) or no symptoms (EPDS < 9); 2) Positive screening of psychotic symptoms using the Psychosis Screening Questionnaire (PSQ); 3) self-reported substance abuse problems. These criteria are consistent with those of other prevention trials (51).

Partners inclusion criteria: 1) The spouse or any other significant person who will accompany the pregnant woman during pregnancy and after childbirth, chosen by the pregnant woman. 2) The pregnant woman has consented to participate in the study.

Participant allocation. Randomization will be centrally controlled by the CHU Ste-Justine Applied Clinical Research Unit (URCA), headed by co-PI [name]. An independent biostatistician will create the randomization scheme, a computer-generated random listing using a 1:1 allocation, according to trial statistician instructions. Random permuted blocks randomization will be used. The randomization list will be WEB-based and completed via REDCap.

Bias protection. With detailed informed consent procedures, it is expected that pregnant women will accept their randomized group allocation. The intervention team will be blinded to the initial level of depressive symptoms. No formal virtual depression prevention intervention program yet exists in Quebec. There will be no interference with usual medical/nursing care, which may include antidepressant medication and/or psychotherapy.

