Counseling interventions received a grade B recommendation from the USPSTF (2), reflecting the low level of risk and high probability of a moderate net benefit. None of the included studies, however, offered virtual counseling and there is very little evidence of the efficacy of virtual prevention interventions. As in all studies where participants report on their mental health, there is always the possibility that participants become more aware of their symptoms. We will minimize risk to participants by taking the following measures. First, at the end of each assessment, there will be a list of resources to manage mental health issues (Appendix M). The list will include contact information for: 1) in Quebec, Integrated University Health and Social Services Centres (CIUSS). These local community health centers offer prenatal classes, telephone call services, and links to psychosocial and mental health services; 2) family physician clinics; 3) obstetric clinics, and; 4) emergency phone numbers and help lines. Second, we will set up a telephone line to answer questions about the study and remind participants of available resources. Third, participants with a positive response on the EPDS self-harm ideation item or scoring above the clinical EPDS cut-off (≥ 13) during screening or follow-up will be notified by a pop-up at the end of the questionnaire. The pop-up will inform them they will receive a phone call from a nurse of our team and encourage them to speak to their doctor and contact resource links (Appendix N). The nurse will make the call within 24 hours to evaluate the suicidal risk and make sure the participant is taken in charge by appropriate health services.

Expected Results and Benefits

[figure not shown]
This project will 1) provide virtual support related to the program content to women with symptoms of depression (moderate severity) in a context where individual medical and psychosocial follow-ups are minimized due to the pandemic; 2) prevent the worsening of depression and anxiety, improve stress management, and potentially improve obstetric outcomes and prevent child development disorders associated with maternal disorders; 3) develop an online economic intervention for pregnant women in situations of social isolation or activity limitations due to various causes (e.g., pandemic, strict rest at home); 4) facilitate the coordination of virtual social support by maternal and child physical health specialists and

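### The primary test counts cases at EPDS > 13, while the declared and powered endpoint is EPDS ≥ 13

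*Combined protocol and SAP*

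**What the plan says.** Planned Analyses is the only section that specifies the primary test. It sets a chi-square comparison, at 3 months, of "the difference in the proportion of women with EPDS in the clinical range (> 13"). It then extends the method to the second time point: "The same approach will be used for the 6-month assessment (secondary outcome").

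Every other statement of the clinical cut-off includes the score 13:

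- Primary outcome: "proportion of women with EPDS scores above the clinical cut-off for depression (EPDS \geq 13").
- Sample size: "20% of women with EPDS ≥ 13 in the control arm versus 10% in the intervention arm".
- Pregnant women exclusion criteria: "EPDS score in the clinical range (≥ 13) or no symptoms (EPDS < 9").
- Risks to Participants: a nurse call follows for women "scoring above the clinical EPDS cut-off (≥ 13) during screening or follow-up".
- Opening background section: "2/3 of these will go on to clinical postpartum depression (EPDS \geq 13").

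The inclusion criteria admit scores 9 to 12, so 13 is the first score above the entry range. No section explains why the analysis would use a different threshold.

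**The concern.** The threshold decides who is an event in the one test run at the 5% level. The EPDS is a 10-item sum from 0 to 30, so > 13 and ≥ 13 differ by exactly the women who score 13. Under the analysis text such a woman is a non-case at 3 and 6 months. Under the outcome definition she is a case, and under Risks to Participants her score prompts a nurse call.

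Two programmers, one working from Planned Analyses and one from the outcome definition, would build different primary datasets. Leaving both versions in the plan also allows the dichotomisation to be settled after results are seen, which pre-specification is meant to prevent.

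**Working it through.** **1. Does the planned N belong to ≥ 13?**

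Inputs from Sample size: 20% vs 10%, both at ≥ 13; two-sided alpha 5%; power 80%; 250 per arm; attrition 10% by 3 months and another 10% by 6 months.

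Two-proportion formula with pooled variance under the null, mean rate 0.15:

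n = [1.960 × √(2 × 0.15 × 0.85) + 0.842 × √(0.20 × 0.80 + 0.10 × 0.90)]² / 0.10² = (1.4105)² / 0.01 = 198.96, so 199 per arm.

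Attrition as two successive losses: 199 / (0.9 × 0.9) = 246 per arm, 492 in total. As a single 20% loss: 199 / 0.8 = 249 per arm, 498 in total. The plan states 500, so its figure reproduces, and it rests on rates at ≥ 13.

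Power for 20% vs 10% at alpha 5%:

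| Evaluable per arm | Situation | Power |
|---|---|---|
| 250 | no loss | 88.2% |
| 225 | 10% lost (3 months, primary) | 84.6% |
| 202.5 | 10% lost twice | 80.7% |

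The last row reconstructs the sample-size reasoning. It is not the power of the 6-month test, which is secondary and run at 1%.

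**2. How many women could change class?**

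Expected cases at 225 per arm: 225 × 0.20 = 45 and 225 × 0.10 = 22.5, together 67.5. The documents give no share of cases scoring exactly 13. Assuming 5% to 20%: 67.5 × 0.05 = 3.4 and 67.5 × 0.20 = 13.5, so about 3 to 14 women.

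**3. What would a literal > 13 do to power at 225 per arm?**

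Each row rests on an assumption that is not in the documents.

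| Assumption | Rates at > 13 | Power |
|---|---|---|
| 5% of cases in each arm score 13 | 19.0% vs 9.5% | 82.4% |
| 10% | 18.0% vs 9.0% | 80.0% |
| 20% | 16.0% vs 8.0% | 74.4% |
| Normal scores, SD 3.5 | 13.0% vs 5.9% | 73.7% |
| Normal scores, SD 5.5 | 15.3% vs 7.2% | 78.2% |
| Normal scores, SD 8 | 16.7% vs 8.0% | 80.4% |
| 2 percentage points removed from each arm | 18.0% vs 8.0% | 88.6% |

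The normal rows fix the probability above 12.5 at 20% and 10% with a common SD, then recompute the probability above 13.5. Power may fall below 80%, stay near it, or rise.

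**4. Can one woman matter?**

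With invented counts at 225 per arm, 45 vs 29 cases give an uncorrected chi-square p of 0.042. Reclassifying one control woman who scored 13 gives 44 vs 29 and p = 0.055. This shows sensitivity at the margin only; it is not a forecast.

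**The case against.** The strongest reply is that the document settles the matter itself. The outcome section defines the endpoint, the sample size powers it, and the analysis sentence refers back to the primary outcome using a term that the exclusion criteria equate with ≥ 13. An analyst would have to ignore all of that to go wrong, and the supplementary ANCOVA on EPDS scores does not depend on the cut-off. This bears on how likely harm is. It does not remove the contradiction, which sits in the sentence that fixes the event definition for the primary test.

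It may also be that the lower bar of the sign was lost when the PDF was read. That cannot be excluded, but it is not shown: the sign survives in every other section that states the cut-off. If the source document prints ≥, the point falls away.

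Two limits stand. The power scenarios show no consistent direction of harm, so the case rests on the mismatch and not on a power loss. And saying that N is unaffected applies to this correction only. The background's two-thirds progression figure sits uneasily with the 20% control rate, but that is a separate question.

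**Conclusion.** The concern holds. As written, the primary test does not measure the endpoint that was declared and powered, and the 6-month test inherits the error. The contradiction needs no assumption beyond the printed text and the whole-number scale. The weight of the other sections makes ≥ 13 the evident intention.

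Its numerical effect cannot be derived from the documents. Under the assumptions tried, about 3 to 14 women change class, and power at 225 per arm runs from 73.7% to 88.6%, against 84.6% for the declared endpoint. It should be corrected because it defines the primary event and the correction is trivial.

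**What to change.** In Planned Analyses, replace > 13 with ≥ 13 in the primary test, and state that the 6-month test uses the same cut-off. Both then match the Primary outcome and Sample size sections. Make the change before any outcome comparison by arm. Participants are told their allocation, so a reference to unblinding alone would not fix the timing clearly.

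The cost is one symbol and a dated note of the correction. It needs no extra data and, in itself, no change to the 500 or to the stated 80% power.
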